Background: Children with cerebral palsy (CP) frequently struggle with gross motor function, which can interfere with their daily activities and quality of life. Although physiotherapy is an important intervention for improving gross motor function in children with cerebral palsy, adherence to treatment remains a challenge. Physiotherapy programs based on play therapy have been proposed as a new alternative approach to improving treatment adherence and gross motor function in children with cerebral palsy. The aim of this research protocol is to compare the efficacy of play therapy-based physiotherapy programs compared to traditional physiotherapy programs in improving treatment adherence and gross motor function in children with CP GMFCS level III-IV.

Methods: This study will be a randomized controlled trial with a sample size of 64 children aged 4-12 with CP GMFCS level III-IV. Participants will be randomly assigned to receive either a play therapy-based physiotherapy or conventional physiotherapy program 45 minutes twice a week for a period of 16 weeks. Treatment adherence will be measured using a combination of physiotherapy session attendance rates, an adherence logbook and the Goal Attainment Scale (GAS). Gross motor function will be assessed using the Gross Motor Function Measure (GMFM-88) and Quality of life will be measured using the CPQoL-Child, all this will be measured at baseline, 5 weeks, 10 weeks and 16 weeks of intervention and a follow-up at 24 weeks will be done. Data will be analysed using descriptive statistics, independent t-tests, ANCOVA and correlations.

Key words: infantile cerebral palsy, play-therapy, treatment adherence, gross motor function, quality of life and physiotherapy.

3. Título

La eficacia de los programas de fisioterapia basados en la terapia de juego frente a los programas de fisioterapia convencionales para mejorar la adherencia al tratamiento y la función motora gruesa en niños con parálisis cerebral GMFCS nivel III-IV: un protocolo de investigación para un ensayo controlado aleatorizado.

4. Resumen

Antecedentes: Los niños con parálisis cerebral (PC) suelen tener alterada la función motora gruesa, lo que puede interferir con sus actividades diarias y su calidad de vida. Aunque la fisioterapia es una intervención importante para mejorar la función motora gruesa en niños con CP, la adherencia al tratamiento sigue siendo un desafío. Los programas de fisioterapia basados en la terapia de juego se han propuesto como una nueva alternativa para mejorar la adherencia al tratamiento y la función motora gruesa en niños con parálisis cerebral. El objetivo de este protocolo es comprobar la eficacia de los programas de fisioterapia basados en la terapia de juego en comparación con los programas de fisioterapia convencionales para mejorar la adherencia al tratamiento y la función motora gruesa en niños con PC GMFCS nivel III-IV.

Métodos: Este estudio será un ensayo controlado aleatorizado con un tamaño de muestra de 64 niños de 4 a 12 años con PC GMFCS nivel III-IV. Los participantes serán asignados al azar para recibir fisioterapia basada en terapia de juego o fisioterapia convencional 45 minutos dos veces por semana durante un período de 16 semanas. La adherencia al tratamiento se medirá mediante una combinación de tasas de asistencia a las sesiones de fisioterapia, un libro de registro propio y la escala de logro de objetivos (GAS). La función motora gruesa se evaluará mediante el Gross Motor Function Measure (GMFM-88) y la Calidad de vida se medirá mediante el CPQoL-Child, todo esto se medirá al inicio, a las 5 semanas, 10 semanas y 16 semanas de intervención y un se hará seguimiento a las 24 semanas. Los datos se analizarán mediante estadística descriptiva, pruebas t independientes, ANCOVA y correlaciones.

Palabras clave: parálisis cerebral infantil, terapia de juego, adherencia al tratamiento, función motora gruesa, calidad de vida y fisioterapia

5. Background

The term Cerebral Palsy (CP) is a chronic non-degenerative condition of the developing brain which has no cure, few disease-modifying interventions and lots of comorbidities (1–3). Is the most common cause of physical disability in childhood, decreasing quality of life (QoL), and is characterised by a variety of movement and postural disorders, causing activity limitation (4,5).

Multiple etiologies of cerebral palsy affects 2-3 out of every 1,000 live births (1). This interference can happen during the perinatal period including the time during pregnancy (82%), the time of birth (10%), and the first two years of life (8%) (4). Genetic variations, congenital abnormalities, preterm birth, kernicterus, intrauterine growth restriction and infection, hypoxic ischaemia, cerebrovascular insults and accidental and non-accidental brain injury, are known as risk factors that can be combined to cause CP pathways (2,4).

Cerebral palsy is generally diagnosed clinically by identifying and classifying defining features based on movement disorders in the earliest at 6 months (corrected for prematurity), but it is usually confirmed the second year of life when the signs are consistent and neuroimaging (MRI) is available to confirm brain injury (2,4).

The cerebral palsy related movement and tone disorders are very heterogenous and it can be classified topographically with the terms hemiplegia (20-30%), diplegia (55-70%) and quadriplegia (10-15%) and by its motor type divided into four categories (2,4,6):

- Spastic (80%): The damage is originated in the brain and tracks controlling movement. There's a velocity-dependent increased tone (stiff muscles), which is not necessarily continuous, hyperreflexia and upper motor neuron signs.
- Dyskinetic (15%): The damage is originated in the subcortical structure. We can see uncontrolled, repetitive, and involuntary movements that might be stereotyped with a fluctuating muscle tone.

It can be dystonic, characterised by hypertonia and hypokinesia causing stiff movements; or choreoathetoid, characterised by hypotonia and hyperkinesia causing quick and uncontrolled jerky and twisting movements.

- Ataxic (4%): The damage is originated in the cerebellum. There's a loss of the coordination of muscles, of accuracy of movement and unspecific hypotonia. The movement is characterised by atypical force, rhythm, and control of it.
- Mixed pattern (1%): There's no predomination of atypical tone or movement disorder and the most frequent mixed type is a combination of spastic and athetoid patterns.

We can see that this classification doesn't have into account activity and participation limitations as CP must relate to the International Classification of Functioning, Disability and Health (ICF) framework for disability (7). That's why an instrument like the Gross Motor Function Classification System (GMFCS) it's a better tool of classification. This is an age-dependent classification system which describes 5 groups of CP depending on their level of mobility (2,4), without having into account the type of CP, and determines which equipment or mobility aids may the child need in the future in order to provide a prognosis (8). Level 1 denotes minimal disability whereas level 5 denotes complete dependence. Also, there are other functional classification systems that include manual ability, sitting stability, communication skills and eat and drink ability (8).

The principle symptoms of CP are movement disorders caused by spasticity and/or dystonies, resulting in musculoskeletal secondary problems such as hip pain or displacement, weak gross motor ability, hand dysfunction and/or equinus deformity ending up in mobility limitations (2, 4). Moreover, patients with CP may also experience complications not related to movement including intellectual disability (50%), pressure ulcers, incontinence (25%), sleeping, behavioural or emotional disorders (20-25%), vision, hearing and communicating impairments (25%), scoliosis, hydrocephalus, epilepsy (35-62%), cardio-respiratory status or endocrine insufficiency that decrease life expectancy and play as a handicap in the treatment (2,4).

Moreover, there is evidence that socioeconomic status, ethnicity, and gender can influence the incidence (9-13), severity (11) and type of CP (9) as well as affecting their quality of life. Some research attributed this to restricted access to healthcare during pregnancy and childbirth, environmental toxins, and greater rates of premature birth and low birth weight. Three of these research (10, 11, 13) determine that understanding better population groups will improve outcomes over the life course of children with CP and their treatment adherence, but that further investigations might be required to identify how socioeconomic status and ethnicity may influence, and this should be transferred also to planning physiotherapy programs.

The treatments for CP varies depending on the specific symptoms and should be multidisciplinary, but in general is focused on movement disorders and musculoskeletal deformities where physicians and surgical specialist commonly use intramuscular onabotulinumtoxinA, oral or intrathecal muscle relaxants, selective dorsal rhizotomy and hip preventive surgeries, which have to be combined with physiotherapy to obtain maximum benefits (2,4). Nevertheless, before deciding which treatment use is important to discuss expectations with the families to facilitate a tailored multidisciplinary treatment plan based on the patient's individual needs and achievable goals (4).

However, the main treatment is physiotherapy as a way of symptoms management as soon as CP is diagnosed. This intervention will be used especially during childhood and adolescence, to treat movement and balance problems, but also throughout their entire lives. An international practice guideline of improving motor function in CP and published in 2022 (3) determines that there are different modalities and approaches including: massage, weight-bearing, electrical stimulation, treadmill use, stretching, strengthening, endurance training, constraint-induced movement therapy, hippotherapy, virtual reality and biofeedback. Although physiotherapy is the main treatment, there is minimal data supporting on one modality over another due to the difficulty on studying this population (3,4,6).

Children with CP often need intensive and ongoing physical therapy to control their symptoms, improve motor skills, and maintain quality of life. That's why treatment adherence can be a significant challenge in this population, leading to

suboptimal patient outcomes and increasing healthcare costs. Therefore, exploring new interventions that improves treatment adherence and motor function in children with CP is an important research goal.

What it's surprising is that knowing that we are treating children, there's no treatment that includes playing as an intervention. Play is children's natural environment through which they communicate, explore and develop motor skills and social interaction (14). According to some studies (14–17), play therapy is an intervention based on play and its benefits are: increasing the level of oxytocin, enhancing well-being and trust, reinforcing the therapeutic relationship and activating mirror neurons (15); all that providing neuroplasticity and creating new neuronal pathways that helps in improving altered skills like gross motor function is (15). Based on this theory and the fact that physiotherapy programs in children with CP are long lasting and can be boring, exhausting and demotivating, physiotherapy sessions should be more effective and enjoyable if they focused on both the physical and emotional needs of children through play (14,16).

It exists different types of play therapies, but the two most common types of therapeutic play are directed therapeutic play and non-directed therapeutic play. In the directed type, the therapist directs the play and its objectives, determining the theme and content of the play process as well as the activity in which the child will participate (14,16). In the non-directed type, the environment and materials are still selected by the therapist with the same purpose as before, but now is the child who decides the rest of the activity making it spontaneous (14,16). The choice of which type use should be individualized so the physiotherapist who works with the child should plan therapy sessions around his or her motivations and limitations (16).

Having this into account, play therapy-based physiotherapy programs are a relatively new approach to treating children with CP. These programs aim to increase treatment adherence by using play and games to make physiotherapy sessions more enjoyable and engaging for children. While some studies (16-18) have suggested that play therapy-based interventions can improve gross motor function and treatment adherence in children with CP, the evidence base is limited and inconclusive as their methodologies aren't consistent.

A study from 2012 (17) that investigated the efficacy of play therapy combined with conventional therapy in improving hand function ability in children with spastic diplegic cerebral palsy, concluded that the interventional group showed better outcomes than the group not doing the session based on play therapy. In addition, an integrative review from 2018 (18) studied the use of play therapy in motor rehabilitation in CP. Most of the studies included in this review used computer games and video games and concluded that incorporating play-based activities into the treatment of children with cerebral palsy, when used correctly, is important to encourage motor skill improvement and benefit the therapeutic relationship, making therapy more dynamic and effective.

There's also a thesis from 2016 (16), on which I've based my hypothesis, which determined that play could serve as a mediator and an appropriate developmental approach for children with chronic health conditions (as CP is) who attend physiotherapy sessions in order to achieve physical and emotional changes. Also, this thesis concluded saying that "although the information presented was not sufficient to draw conclusion, it could serve as a first step for new researchers to study it" (16).

So, having into account the most common signs of CP, the role of physiotherapy in its treatment, the duration of the treatment, the benefits of play therapy and the poor evidence that exists about it; the aim of this study is to investigate whether play therapy-based physiotherapy programs are more effective than conventional physiotherapy programs in improving treatment adherence and gross motor function in children with cerebral palsy GMFCS level III-IV. This study will use a randomized controlled trial design to compare the effectiveness of play therapy-based physiotherapy programs and conventional physiotherapy programs in a sample of children with CP.

This study's findings will have important implications for clinical practice, as they may inform the development of more effective and engaging physiotherapy interventions for children with CP, potentially leading to improved treatment adherence and better gross motor function outcomes which may increase consequently QoL. All in all, I'm sure this protocol of investigation is the first step of something that has been highly requested in the recent years.

6. References

7.1. Research Question

Are play therapy-based physiotherapy programs more effective than conventional physiotherapy programs in improving treatment adherence and gross motor function in children with cerebral palsy GMFCS level III-IV?

7.2. Hypothesis

Play therapy-based physiotherapy programs are more effective than conventional physiotherapy programs in improving treatment adherence and gross motor function in children with cerebral palsy GMFCS level III-IV.

8. General and Specific Objectives

8.1. General Objective

To compare the effectiveness of play therapy-based physiotherapy programs versus conventional physiotherapy programs in improving treatment adherence and gross motor function in children with cerebral palsy GMFCS level III-IV over a 24-week period.

8.2. Specific Objectives

- I. To compare treatment adherence among children receiving game-based physiotherapy and those receiving conventional physiotherapy.
- II. To evaluate improvements in gross motor function among children receiving game-based physiotherapy and those receiving conventional physiotherapy.
- III. To compare quality of life between children receiving game-based physiotherapy and those receiving conventional physiotherapy.
- IV. To identify potential factors that may influence quality of life, treatment adherence, and improvements in gross motor function in both treatment groups.

9. Methodology

9.1. Design

This study will be a randomized controlled trial (RCT) comparing the effectiveness of play therapy-based physiotherapy programs with conventional physiotherapy programs in improving treatment adherence and gross motor function in children with CP GMFCS level III-IV. Owing to the nature of the intervention, this is a prospective study and participants and physiotherapists will not be able to be blinded to group allocation. However, to minimise the risk of bias, outcome assessors will be blinded to group allocation.

9.2. Participants, Recruitment and Criteria of Selection

9.2.1. Participants

The participants of this research will be children with CP GMFCS level III-IV, aged 4 to 12 years and receiving physiotherapy services.

For the sample size ([Annex I](#)), help will be requested from a statistician, and it will depend on factors such as the expected effect size based on previous studies or clinical knowledge, the level of statistical power desired and the level of significance. For example, knowing that similar studies have a sample size of 30, which is always their limitation, a medium effect size is expected, a power of 80% is desired and 0.5 is considered as the level of significance, a sample size of around 64 participants (32 in each group) might be appropriate. However, this sample size might need to be adjusted based on the recruitment rate, dropout rate, and effect size observed during the study.

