9.6. Data Analysis

All data collected from the assessments, questionnaires and the logbook will be analysed using appropriate statistical methods with the help of an expert statistician to achieve the aims of this research protocol. The statistical analyses will be conducted using a statistical software package such as JASP and the statistical significance will be set at p-value <0.05 and CI (Confidence Interval) 95%. When p-value $< 0,05$, the null hypothesis (H_0) will be rejected meaning that the results are statistically significant. The H_0 is: There is no significant difference between the effectiveness of play therapy-based physiotherapy programs and conventional physiotherapy programs in improving treatment adherence and gross motor function in children with cerebral palsy GMFCS level III-IV.

After collecting all data, it will be placed into a spreadsheet for basic data cleaning and categorization ([Annex V](#)). Descriptive statistics (e.g., mean, median, standard deviation, range...) will be calculated to summarize quantitative variables such as age, attendance rate, treatment adherence logbook, GAS score, GMFM-88 score and CP QOL-Child score, while frequency distributions and percentages will be used to summarize categorical variables such as gender, GMFCS level (III or IV), socio-economic status, ethnicity, and type of intervention. All that describes the participants' demographic and baseline characteristics, as well as analyses the distribution of the variables of interest.

Statistical analysis will be done to test the hypothesis using appropriate methodologies based on the data distribution and characteristics. For quantitative variables, t-tests or ANOVA may be used to compare means between the two groups (play therapy-based physiotherapy versus conventional physiotherapy). However, for categorical variables, chi-square or Fisher's exact test might be used, but in this study, it may not be necessary as the hypothesis doesn't include categorical variables.

Moreover, linear regression analysis may be used to investigate the association between treatment adherence and gross motor function while to identify predictors of treatment adherence, gross motor function and quality of life, including age, gender, GMFCS level, social-economic status, ethnicity, and treatment group so potential confounding variables will be controlled for in the

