15.1. Annex I: Calculation of the Sample Size

For calculating the sample size the following formula have been used (F, G):

$$n = \frac{2SD^2(Z_{\alpha/2} + Z_{\beta})^2}{d^2}$$

Where:

- **n** = sample size
- **Z $\alpha/2$** = the Z-score for the desired level of significance so for 95% confidence level $\alpha=0.05$, $Z_{\alpha/2} = 0.05/2 = 0.025$. This from Z table is **1.96**.
- **Z β** = the Z-score for the desired statistical power so for 80% power where β is 0.20, $Z_{\beta} = 0.8416$ from the Z table.
- **SD** = the estimated standard deviation of the outcome variable based on other studies is **2.43** (18).
- **d** = the effect size (difference in means divided by the pooled standard deviation) taking into account the previous study (18) it will be **1.2**.

Having into account all this, the sample size should be:

$$n = \frac{2SD^2(Z_{\alpha/2} + Z_{\beta})^2}{d^2}; n = \frac{2 \times 2.43^2 (1.96 + 0.8416)^2}{1.2^2}; n = 64.37 \approx 64 \text{ participants}$$

Sample size = 64 participants.

Remember that this sample size may need to be adjusted by a statistician based on factors such as recruitment rate and expected dropout rate.

F: Charan J, Biswas T. How to calculate sample size for different study designs in medical research? Indian J Psychol Med. 2013 Apr;35(2):121-6.
G. Kadam P, Bhalerao S. Sample size calculation. Int J Ayurveda Res. 2010 Jan;1(1):55-7.

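### Section 9.2.1 prints the significance level as 0.5, against 0.05 in Annex I and Section 9.6; correcting it leaves the 64 unchanged, but the 80% power beside it must also be restated

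*Protocol*

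**What the plan says.** Three places in the protocol state a significance level.

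- **Section 9.2.1 (Participants)**, the main-text account of the sample size: "a power of 80% is desired and 0.5 is considered as the level of significance, a sample size of around 64 participants (32 in each"; the bracketed 32 is per group. The sentence is offered as an example and is hedged. It also assumes a medium effect, without a number. The paragraph refers the reader to Annex I.
- **Annex I (Calculation of the Sample Size)** defines its first Z value as "the Z-score for the desired level of significance so for 95% confidence level", sets alpha at 0.05, halves it for a two-sided test and uses 1.96. Power is again 80%, with Z = 0.8416. The SD is 2.43 and d is 1.2. The result is 64.37, rounded to 64 participants.
- **Section 9.6 (Data Analysis)** fixes the decision rule: "the statistical significance will be set at p-value <0.05 and CI (Confidence Interval) 95" per cent. It then repeats that the null hypothesis is rejected when p is below 0.05.

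The value 0.5 appears only in Section 9.2.1.

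**The concern.** The significance level is both an input to the sample size and the threshold for the trial's conclusions, which the protocol says will rest on statistical significance. Two values a factor of ten apart cannot both stand in current text.

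Section 9.2.1 is where an ethics reviewer or reader looks to see how the trial is sized. Sections 9.2.1 and Annex I both leave the number open to adjustment, Annex I by a statistician. Someone recalculating from the main text would start from the wrong alpha. The sentence also sets alpha, power, effect and N side by side, so they should be mutually consistent.

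**Working it through.** **Inputs.** SD = 2.43, d = 1.2, Z for power = 0.8416 (all Annex I); alpha = 0.05 (Annex I, Section 9.6) or 0.5 (Section 9.2.1); 32 per group (Section 9.2.1). The normal quantile is 1.96 for two-sided alpha 0.05 and 0.6745 for two-sided alpha 0.5.

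**Step 1: reproduce the plan's figure.** The Annex I formula is n = 2 × SD² × (Zα/2 + Zβ)² / d².

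- 2 × 2.43² / 1.2² = 11.8098 / 1.44 = 8.2013
- (1.96 + 0.8416)² = 7.8490
- n = 8.2013 × 7.8490 = **64.37**

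This matches Annex I, so the 64 was computed at alpha 0.05, the level that Section 9.6 applies.

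**Step 2: the same formula at the alpha in Section 9.2.1.**

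- (0.6745 + 0.8416)² = 2.2985
- n = 8.2013 × 2.2985 = **18.85**, that is 19 per arm or 38 in total
- Taken as one-sided, alpha 0.5 gives 6 per arm

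Neither gives 64, in total or per arm.

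**Step 3: what n counts.** The factor 2 × SD² / n is the variance of a difference between two means that each rest on n children. The formula therefore gives n **per arm**. At alpha 0.05 the inputs call for 65 per arm after rounding up, or 130 in total. Section 9.2.1 uses 64 as the total.

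**Step 4: power with 32 per group.** Annex I describes d as a standardised effect but enters 1.2 beside an SD of 2.43, as a raw difference. Read as the formula uses it, the standardised difference is 1.2 / 2.43 = 0.494. In the normal approximation, the expected test statistic is 0.494 × √(32/2) = 1.975.

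| Two-sided alpha | Calculation | Normal approximation | t-test |
|---|---|---|---|
| 0.05 | Φ(1.975 − 1.96) | 51% | 49% |
| 0.5 | Φ(1.975 − 0.6745) | 90% | 91% |

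The stated 80% fits neither row. It does fit 64 **per group** at alpha 0.05: the expected statistic is 0.494 × √(64/2) = 2.79, and Φ(2.79 − 1.96) is about 80% (t-test 79%).

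**Step 5: sensitivity to the effect.**

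- If the medium effect in Section 9.2.1 is taken as a standardised 0.5 (an assumption, since no number is given), power with 32 per group at alpha 0.05 is 50% to 52%.
- If 1.2 really were a standardised effect, 11 per arm would suffice and 32 per group would have over 99% power. That is not how the formula uses 1.2, and it would not give 64.

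**The case against.** The strongest reply is that this is one misprinted figure with no consequence. The sentence is hedged and introduced as an example, its paragraph points to Annex I where 0.05 and 1.96 are written out, and Section 9.6 states the threshold twice. No number in the protocol was computed at 0.5. A level of 0.5 is implausible on its face, so the intended value is not in doubt.

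Most of this stands, and it rules out three stronger readings that a reader might infer:

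- **That the sample size comes from a different rule than the analysis.** Step 1 shows that it does not: 64.37 is the result at 0.05.
- **That the trial would accept a 50% false-positive rate.** That would require setting aside both the analysis section and the worked calculation.
- **That the low power follows from the 0.5.** It follows from using a per-arm n as the total, and would be the same had 0.05 been printed.

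What does not stand is that nothing needs doing. The figure is in the current main-text account of the trial's size and contradicts two other sections. Changing that one figure alone would still leave 80% power beside 32 per group, which the protocol's own inputs do not support.

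**Conclusion.** The contradiction is real and narrow. Section 9.2.1 states a significance level ten times the one used in Annex I and Section 9.6, most likely through a slip. Correcting it to 0.05 alters neither the Annex I result nor the analysis. As printed, the sentence's figures are incompatible: its alpha with Annex I's inputs would need about 38 children in total, not 64.

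A second error in the same sentence has a separate cause. At 0.05, 32 per group gives about 49% to 51% power before any dropout, not 80%, because the Annex I result is per arm. This figure assumes a two-sided comparison of two means with equal groups, SD 2.43 and 1.2 as a raw difference; the reading of 1.2 matters most, as Step 5 shows.

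**What to change.** In Section 9.2.1, replace 0.5 with: a two-sided significance level of 0.05. In the same sentence, state the power that 32 per group has at that level, together with the difference and SD it assumes. On Annex I's inputs as the formula uses them, this is about 50% in place of 80%.

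The cost is two figures and a short statement of assumptions. The Annex I result, the analysis in Section 9.6 and the conduct of the trial are unaffected.

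The change should say plainly that the power shortfall comes from the per-arm result being used as a total, so that it is not taken to be settled by correcting alpha. Whether to enlarge the trial (about 130 children for 80% power on these inputs) or to justify 64 is a separate decision with its own cost.
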